5.6. Protocol Violations and Deviations

A major protocol violation or deviation may affect the interpretation of study results or the patient's rights, safety or welfare. Major violations and deviations are defined as follows:

- Mis-randomizations (defined as patients who received the opposite treatment)
- Non-compliance of Inclusion and Exclusion criteria (to be identified through review of data sourced from the site monitoring database)
- Significant Good Clinical Practice (GCP) non-compliance sites (to be identified by [REDACTED] as sites which have been closed due to scientific misconduct and/or serious GCP non-compliance)

Patients with Non-compliance of Inclusion and Exclusion criteria or Significant Good Clinical Practice (GCP) non-compliance sites could be excluded from PP population. Also, Mis-randomizations will be excluded from PP, PK and Pharmacodynamic population. The major protocol violations and deviations will be summarized by treatment group for the ITT population and will also be presented in a listing.

5.7. Missing Values

In order to evaluate the impact of missing data on the efficacy primary endpoint results, additional analyses with tipping point analyses will be conducted for the primary efficacy endpoint for ITT population.

Tipping point analyses will be conducted under Missing Not at Random (MNAR) scenarios. Imputed values (patients with no response evaluation result or 'Unable to assess') as responder will be shifted gradually by treatment groups to make MNAR scenarios. 90% CI of the difference between two proportions (CT-P10 group and Rituxan group) will be calculated using asymptotic methods, and scenarios will be displayed by shift table.

All the scenarios will be also provided using 2-dimensional plot.

6. PATIENT DISPOSITION

The number of patients who were screened will be displayed. The number of screening failures and the primary reason for screening failure will also be summarized.

The number of patients who have been randomized, the number and percentage of patients who have initiated study treatment, have discontinued the study treatment, and have completed the study treatment will also be displayed for prior to Maintenance Cycle 3 and up to MP1 in the ITT population, and MP2 in the ITT population – 2nd Maintenance Period subset.

- A patient will be considered to have failed the Screening if the date is recorded on the ‘Screening Failure’ page of eCRF.
- A patient will be considered to be randomized if the date of randomization is recorded on the ‘Randomization’ page of eCRF. The randomization date recorded in this eCRF page will be used as the date of randomization for further analyses described in this document.
- A patient will be considered to have initiated study treatment if actual administered dose or the kit number of study drug are recorded on the ‘Study Drug Administration CT-P10/RITUXAN’ page of eCRF of the Induction Study Period. MP2 will be considered to be initiated if actual administered dose or the kit number of study drug is recorded on eCRF at Cycle 7 of the Maintenance Study Period.
- A patient will be considered to have completed study treatment prior to Maintenance Cycle 3 if the patient has initiated treatment in the Induction Study Period and not recorded to have discontinued study treatment prior to Maintenance Cycle 3 visit date on ‘Study Termination’ page of eCRF. A patient will be considered to have completed up to MP1 if the patient recorded ‘Yes’ was collected in question ‘Did the patient complete the 1st year Maintenance Study Period’ on the eCRF page of ‘Study Treatment Termination’. A patient will be considered to have completed MP2 if the patient has initiated MP2 and recorded to have completed all study periods on ‘Study Treatment Termination’ page of eCRF.
- A patient will be considered to have discontinued study treatment prior to Maintenance Cycle 3 if it is recorded that the patient did not complete prior to Maintenance Cycle 3 visit date on the ‘Study Treatment Termination’ page of eCRF. A patient will be considered to have discontinued study treatment up to MP1 if the patient did not answer ‘Yes’ to question ‘Did the patient complete the 1st year Maintenance Study Period’ on the ‘Study Treatment Termination’ page of eCRF. A patient who have discontinued after completion of MP1 and before initiation of MP2 will be considered separately. A patient

will be considered to have discontinued study treatment in MP2 if the patient have initiated MP2 and ‘No’ is recorded to question ‘Was the patient offered additional treatment by 12 cycle in 2nd year Maintenance Period?’ on ‘Study Treatment Termination’ page of eCRF.

The number and percentage of patients who have completed MP1 and not entered MP2, who discontinued each period (for prior to Maintenance Cycle 3, up to MP1, and MP2) will also be displayed by primary reason for discontinuation. Time on study drug prior to discontinuation in each category which is calculated as (Last dose date – First dose date + 1) will also be summarized with descriptive statistics.

The number and percentage of patients who entered the Follow-up Period will be summarized. A patient will be considered to have entered the Follow-up Period if the patient has visited at the first Follow-up visit schedule. Reason for ending participation in the study will also be summarized, as evidenced in the ‘End of Study Participation’ page of eCRF. Deaths will be summarized by reasons using the data reported on ‘Study Treatment Termination’ page or ‘Survival Status’ page of eCRF.

The patient disposition data collected will be listed for the ITT population. A listing of patients reported as screening failures will also be provided.

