 - The first year of Maintenance Period (MP1) consists of 6 cycles of maintenance therapy (Maintenance Cycles 1 to 6) and the second year of Maintenance Period (MP2) consists of 6 cycles of maintenance therapy (Maintenance Cycles 7 to 12). After MP1, once the similarity between study drugs is confirmed, additional treatment with CT-P10 will be offered to all patients who have completed MP1 at discretion of the investigator.
 - The EOT3 visit will occur 8 weeks (± 7 days) after the last dose of study drug administration in the Maintenance Study Period.
 - Patients who complete the Maintenance Study Period will enter the Follow-up Period. A patient will be considered as having completed the study treatment if:
 - The patient could have entered but did not continue on the MP2 and completed all visits of the MP1 (total 6 cycles).
 - The patient continued on the MP2 and completed all visits of the MP1 and MP2 (total 12 cycles).
 - If a patient withdraws before the completion of the Maintenance Study Period, the patient will enter the Follow-up Period, provided patient consent has not been withdrawn.
 - If a patient is terminated within 6 months from Day 1 of Cycle 1 of the Induction Study Period, the EOT3 visit will occur within 4 to 8 weeks (± 7 days) after the last dose of study drug administration in the Maintenance Study Period.
- Follow-up Period (up to 27 months from Day 1 of Cycle 1 of the Induction Study Period for the last enrolled patient):
 - During the Follow-up Period, patients will be monitored every 6 months (± 2 weeks) for disease status until treatment with new anticancer therapy or disease progression, and

every 3 months (± 2 weeks) for survival and salvage treatment until death or study termination.

The end of study is defined as the date of the database is locked. The schedule of events is presented in [APPENDIX 1](#).

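### SAP section 6 derives discontinuation in the second maintenance year (MP2) from a 'No' to an 'offered' question which, read literally, no patient who started MP2 could answer 'No'

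*SAP*

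**What the plan says.** SAP section 6 sets three rules for MP2.

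- **Initiated:** "MP2 will be considered to be initiated if actual administered dose or the kit number of study drug is recorded on eCRF", the visit in question being Maintenance Cycle 7.
- **Completed:** "A patient will be considered to have completed MP2 if the patient has initiated MP2 and recorded to have completed all study periods", taken from the 'Study Treatment Termination' page.
- **Discontinued:** a patient "will be considered to have discontinued study treatment in MP2 if the patient have initiated MP2" and the answer 'No' is recorded, on the same page, to the question "Was the patient offered additional treatment by 12 cycle in 2nd year Maintenance Period".

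Section 4 describes how patients reach MP2: "additional treatment with CT-P10 will be offered to all patients who have completed MP1 at discretion of the investigator". The protocol synopsis, under Route of Administration, uses the word in the same way. For patients who go on to MP2, section 4 defines completion of study treatment as "The patient continued on the MP2 and completed all visits of the MP1 and MP2 (total 12 cycles").

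For the first maintenance year (MP1), section 6 relies on a question that asks directly whether the patient completed that year. Any answer other than 'Yes' counts as discontinued. Patients who stop after MP1 but before MP2 starts are handled as a separate category.

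**The concern.** The two conditions for MP2 discontinuation pull against each other. The first requires that the patient was dosed, or had a kit recorded, at Cycle 7. The second, in its ordinary sense, requires that the patient was not offered the treatment. Since section 4 places the offer before MP2, the first condition implies a 'Yes' to the second.

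The patient whom the count is meant to capture is one who starts MP2 and stops before Cycle 12. On the literal wording that patient falls outside both the discontinued and the completed group.

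At stake are the MP2 columns of the disposition summary: the all-reason number of discontinuations, the breakdown by primary reason, and time on study drug before discontinuation. Section 5.4.1.2 labels the MP2 groups 'Switched to CT-P10' and 'CT-P10 Maintenance', so these outputs describe, side by side, how many patients stopped after the change from Rituxan and how many stopped while continuing CT-P10, and why.

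**Working it through.** The plan gives no figure on this point, so the check is to apply the section 6 rules to each kind of patient who starts MP2.

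Inputs: the initiation, completion and discontinuation rules (SAP section 6), the meaning of 'offered' and the 12-cycle definition of completion (SAP section 4). An early stopper is taken as not recorded as having completed all study periods.

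| Reading of the question | MP2 starter | Answer | Completed? | Discontinued? |
|---|---|---|---|---|
| Literal: was MP2 treatment offered? | treated through Cycle 12 | Yes | yes | no |
| Literal | stops early | Yes | no | **no** |
| Through Cycle 12: was treatment given up to Cycle 12? | treated through Cycle 12 | Yes | yes | no |
| Through Cycle 12 | stops early | No | no | yes |
| Either | stops early | blank | no | **no** |

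Let E be the number of MP2 starters who stop early, and B the number of those whose answer is blank.

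- Literal reading: discontinued = 0, unclassified = E.
- Through-Cycle-12 reading: discontinued = E − B, unclassified = B.
- In both cases initiated = completed + discontinued + unclassified, so the table adds up only if the unclassified number is zero.

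No other category picks up the unclassified patients. The separate category for stopping between the two years ends when MP2 starts. A patient who was never offered MP2 might have a 'No' recorded, but did not initiate MP2 and so is not in this count.

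The MP1 rule does not have this problem. Its question is about completion, and a blank falls into discontinued because only 'Yes' counts as completed. Within MP1 the two groups are complementary by construction. The MP2 rule requires a recorded 'No', and nothing in the SAP ties it to the completion rule.

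**The case against.** The strongest reply is that the literal reading ignores part of the question. The words 'by 12 cycle' do nothing if the item asks only about the initial offer. The item sits on the termination page, and entry to MP2 already has its own eCRF page (section 5.4.1.2). Pairing initiation with a recorded 'No' makes sense only if patients who started can answer 'No'. All this suggests that the item was meant to ask whether treatment was given through Cycle 12. On that reading the rule works, blanks apart. This carries weight, and the flaw may be one of wording only. But the SAP does not state that meaning, and the eCRF version it cites in section 2 is not available to settle it.

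A second reply is that the SAP does not name the item behind "completed MP2 if the patient has initiated MP2 and recorded to have completed all study periods". It could be this same question, with 'Yes' meaning completed. Under the through-Cycle-12 reading the two rules would then be complementary except for blanks. That also stands as a possibility. Under the literal reading, however, it would move early stoppers into the completed group, so the wording would still misclassify them.

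A third reply is that other outputs cover part of the loss. TEAEs leading to permanent discontinuation are summarised for the Safety population's MP2 subset (sections 13.1 and 13.1.4), doses given and reasons for doses not given are tabulated by visit (section 9.2), and disposition data are listed (section 6). This is correct. It leaves the all-reason count, the reasons other than adverse events as a disposition summary, and time on drug.

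**Conclusion.** The derivation rule does not work as literally worded, and under any reading it leaves an early stopper with a blank answer unclassified if completion is not recorded. The point is minor. It touches only descriptive MP2 disposition outputs and changes no endpoint, analysis population, equivalence margin or test. Stops due to adverse events also appear in the TEAE-discontinuation tables.

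A reader might infer that every MP2 discontinuation will be missed and that the table of reasons will be empty. The documents do not support that. It follows only from the literal reading, and how sites actually answered depends on an eCRF and completion instructions that are not available.

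Nor can a number of patients be given. The documents state neither the proportion expected to enter MP2 nor the proportion expected to stop early, so any count would reflect assumed rates and not the flaw itself.

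**What to change.** Replace the MP2 discontinuation rule in SAP section 6 with a definition built on the SAP's own completion rule. A patient is discontinued in MP2 if MP2 was initiated, study treatment has ended, and the patient is not recorded on the 'Study Treatment Termination' page as having completed all study periods (12 cycles). Cross-check this against the Cycle 12 dosing record, which guards against the completion record itself resting on the ambiguous question.

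The condition that treatment has ended is needed because section 2 allows additional CSRs. Without it, patients still receiving MP2 treatment at such a cut-off would be counted as discontinued. Show them in a separate row. At the final CSR, when all patients have completed or terminated, verify in each MP2 group that completed + discontinued = initiated.

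The cost is a short amendment to one SAP paragraph and one programming check. The definition uses the termination page and dosing records that section 6 already relies on, and it classifies patients correctly whichever meaning of 'offered' was intended.

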7. DEMOGRAPHICS, BASELINE AND BACKGROUND CHARACTERISTICS

7.1. Demographics

The following patient demographic measures recorded in eCRF will be tabulated for the ITT population: age (years); sex (Male, Female); race (American Indian or Alaska native, Asian, Black or African American, Native Hawaiian or other pacific islander, White or Caucasian, Not Allowed by Investigator Country Regulations, or Other); fertility status (Pre-Menarche, Surgically Sterilized, Post-Menopausal [last menstrual period more than 1 year], Potentially Able to bear Children, or Other); region (Asia Pacific, Europe, North America, or Other); Ethnicity (Hispanic or Latino, Not Hispanic or Latino, Not Reported, or Unknown); and height (cm), weight (kg) , body surface area (BSA [m²]) and Eastern Cooperative Oncology Group (ECOG) performance status as recorded at the Screening.

Age will be automatically calculated in the eCRF system based on the date of the informed consent signed, the year of birth and information on date of birth passed or not. All demographics data will be listed for the ITT population.

7.2. Medical History

Medical history is captured at the Screening and will be coded using Medical Dictionary for Regulatory Activities (MedDRA Version 18.1 or later). Medical history will be summarized by treatment group, system organ class (SOC) and preferred term (PT) displaying the number and percentage of patients for the ITT population.

A listing of medical history will be provided by treatment group for the ITT population.

7.3. Pathological Diagnosis, Ann Arbor Staging and FLIPI Score

At the Screening, information related to patients' disease status will be collected. All data related to disease status will be analyzed for the ITT population.

7.3.1. Pathological Diagnosis

Pathological diagnosis assessment results will be obtained from independent central pathologic review, and additional results from local assessment may be available. Pathological diagnosis data from central independent review will include following: Follicular CD20+ Lymphoma Diagnosis; Follicular Lymphoma Grade at Screening; CD3, CD10, CD20, B-cell Lymphoma (BCL)-2 and BCL-6; Fluorescence In Situ Hybridization (FISH) result and comments if applicable. Local assessment result will include following: Disease duration of lymphoma; Follicular CD20+ Lymphoma Diagnosis; Follicular Lymphoma Grade examined both at initial diagnosis and Screening; and spleen size (cm) obtained at Screening by CT scan for organ enlargement assessment.

Disease duration (Months) will be calculated as: $(\text{First dose date} - \text{Initial diagnosis date} + 1) / 30.4$. Incomplete initial diagnosis date will be imputed using the latest possible date. If the day is missing (i.e. XXMAR2017) the date will be set to the last day of the month (i.e. 31MAR2017). If the day and the month are missing (i.e. XXXXX2017) the date will be set to 31st December (i.e. 31DEC2017). If the imputed initial diagnosis date is later than first study drug administration date, it will be imputed as the first study drug administration date. If the whole date is missing, the date will not be imputed and disease duration will not be calculated.

Pathological diagnosis data will be summarized in a table by treatment group. All central and local assessment results will be presented in separate listings. FISH results and comments from central review will only be presented in listings separately.

7.3.2. Ann Arbor Staging

Ann Arbor stage, the principal stage and modifiers, from both at initial and screening diagnosis will be summarized and listed by treatment group. If a patient has more than one modifier, the patient will be counted in each modifier category.

7.3.3. FLIPI Score

Follicular Lymphoma International Prognostic Index (FLIPI) Score (0 to 5) will be tabulated along with each component by treatment group. All FLIPI Score data will also be listed.

7.4. Inclusion and Exclusion Criteria

Details of inclusion and exclusion criteria can be found in Sections 4.1.1 and 4.1.2 of the protocol (CT-P10 3.4) respectively. Inclusion and exclusion criteria for each patient will be presented in separate listings for the ITT population. A number of inclusion and exclusion criteria may be modified during protocol revisions. The listing will indicate which version of protocol the subject was recruited under and hence which criteria applied.

7.5. Other Baseline Characteristics

At the Screening, assessments for following viral serology parameters will be conducted:

- Hepatitis B Surface Antigen (HBsAg)
- Hepatitis B Surface Antibody (HBsAb)
- Hepatitis B Core Immunoglobulin (HBcIg)
- Hepatitis B Virus DNA test
 - DNA test will be conducted for patients with negative HBsAg, negative or positive HBsAb, and positive HBcIg.
- Hepatitis C Antibody
- Human Immunodeficiency Virus 1 (HIV-1) and HIV-2

A listing will present viral serology data for the ITT population. Screening results of viral serology tests will be summarized in a table for the ITT population. For HIV-1 and HIV-2, summarization will be combined as following: ‘Positive (at least one positive)’, ‘Negative (at least one negative with no positive)’, and ‘Both Not Done’.

8. BIOMARKERS

A blood sample for evaluation of Fc γ R genotype (Fc γ RIIa, Fc γ RIIIa and/or any necessary genotypes) will be collected according to the [APPENDIX 1](#). The Fc γ R genotype will be evaluated as secondary endpoints.

The number and percentage of patients per genotype will be tabulated by treatment group for the ITT population. The denominator for all percentages will be the number of patients who agreed to collect blood samples for biomarker assessment. A listing will also be presented.

9. MEDICATIONS AND TREATMENTS

9.1. Prior and Concomitant Medications

All medications will be coded according to the World Health Organization drug dictionary (WHO DD September, 2015 or later). All prior anticancer therapies and concomitant medications should be recorded in the eCRF. For the purpose of inclusion in prior and/or concomitant medication tables, incomplete medication start and stop dates will be imputed as follows:

If the stop date is partial or missing, the following rules will be applied.

- If the day is missing (e.g. XXFEB2017), the last day of the month (e.g. 28FEB2017) will be assumed.
- If the day and month are missing (e.g. XXXXX2017), December 31st will be assumed.
- If the stop date is missing (e.g. XXXXXXXXXX), the date will be considered as ‘Continuing’.

In the case of the death of a patient, the stop date will be imputed as the date of death if the imputed stop date is after the date of death.

If the start date is partial or missing, the following rules will be applied. If the stop date is incomplete, imputed stop date will be used instead of reported stop date.

- If the day is missing (e.g. XXFEB2017), the month and year of the partial date will be compared to the date of the first infusion.
 - If the month and the year are equal for both dates, the start date will be imputed as the earlier date of: (i) the date of the first infusion, or (ii) the recorded/imputed stop date

of the medication. If the recorded/imputed stop date is missing, the start date will be imputed as the date of the first infusion.

- If the month or year is not equal for both dates, the start date will be imputed as the first day of the month (e.g. 01FEB2017).
- If the day and month are missing (e.g. XXXXX2017), the year of the partial date will be compared to the date of the first infusion.
 - If the years are equal for both dates, the start date will be imputed as the earlier date of: (i) the date of the first infusion, or (ii) the recorded/imputed stop date of the medication. If the recorded/imputed stop date is missing, the start date will be imputed as the date of the first infusion.
 - If the years are not equal for both dates, the start date will be imputed as the first day of January of the year (e.g. 01JAN2017).
- If the start date is missing (e.g. XXXXXXXXX), the start date will be imputed as the earlier date of: (i) the date of first infusion, or (ii) the recorded/imputed stop date of the medication. If the recorded/imputed stop date is missing, the start date will be imputed as the date of first infusion.

Medications will be classed as either prior or concomitant medication. A prior medication is defined as any medication where the start and stop dates or imputed start and stop dates are before the date of first infusion. A concomitant medication is defined as any medication that has an actual or imputed stop date on or after the date of first infusion or missing. The start date of a concomitant medication can be before or after the date of the first infusion.

Prior and concomitant medications will be tabulated separately by treatment group, drug class (using Anatomical Therapeutic Chemical [ATC] level 2), and preferred term, for the Safety population. The total number of prior or concomitant medications and the number and percentage of patients with at least one prior or concomitant medication will be summarized.

Concomitant medications will be presented for Overall, up to MP1 and MP2, defined as follows: a concomitant medication with a start date prior to the date of first infusion in MP2, or concomitant medication for those patients who did not enter MP2 will be included up to MP1. Otherwise, concomitant medication for those patients who have entered MP2 will be summarized in MP2 for the Safety population – 2nd Maintenance Period subset if the concomitant medication has a start date on or after the date of first infusion in MP2.

All prior and concomitant medications will be presented in separate listings by treatment group for

the Safety population. Patients who are included in the Safety population – 2nd Maintenance Period subset will be flagged in listings.

